9.5. Laboratory Evaluations

[figure not shown]
Non-fasting samples will be collected for serum chemistry, hematology, coagulation (prothrombin time), and urinalysis. In addition, for women of child bearing potential, a serum pregnancy test will be collected. If a urine pregnancy test is positive, a serum pregnancy test will be performed to confirm. The hematology tests that will be collected are: Hemoglobin, Hematocrit, Leukocyte count (total), Leukocyte count (differential), Red blood cell count, and Platelet count. Serum chemistry tests that will be collected are: Glucose, Total bilirubin, Alanine aminotransferase, Aspartate aminotransferase, Alkaline phosphatase, Blood urea nitrogen, Pregnancy (women of childbearing potential at Screening), Potassium, Sodium, Calcium, Carbon dioxide (Bicarbonate), Chloride, Creatinine, Total protein. Urinalysis tests that will be collected are: Specific gravity, pH, Glucose, Protein, Blood, Bilirubin, and Ketones. Other additional tests that will be collected are: Prothrombin time, urine pregnancy for women of childbearing potential, serum pregnancy test at end of study if urine pregnancy test is positive, [REDACTED]. Summary tables and listings will report laboratory results using Système International (SI) units.

This document is confidential.

[figure not shown]
Summary statistics for observed values and changes from baseline will be provided for chemistry, hematology, coagulation, [REDACTED] by dose and treatment cycle for each visit. Summary statistics for observed urinalysis values will be provided by dose and treatment cycle for each visit.

Shift tables will also be provided for shift from Baseline to Week 12 of each treatment cycle and shift from Baseline to Week 52/End of Study. Shift tables will be based on normal ranges and results will be reported as low, normal, or high. For urinalysis values, results will be reported as normal or abnormal. Summaries will be provided by dose and treatment cycle.

A listing will be provided for all laboratory values at all visits. A listing of all out-of-range or clinically significant laboratory test results at any evaluation will be provided. Determination of clinical significance for all out-of-range laboratory values were to be made by each investigator and will be included in the listing.

This document is confidential.

This document is confidential.

9.7. Vital Signs

Vital signs include weight, body temperature, respiration rate, sitting radial pulse rate, and sitting systolic and diastolic blood pressure. Height is collected at the Screening visit only. Body Mass Index (BMI) will be computed using the weight at each visit and height at Screening: $BMI = \text{weight (kg)} / \text{height (m)}^2$.

Vital signs will be summarized by dose and treatment cycle for each visit. All vital signs will be included in a listing.

9.8. ECG

A standard 12-lead ECG will be performed after the subject has rested quietly in the supine position for at least 10 minutes. The ECG data will be submitted to a central reader for review.

A summary of the overall ECG interpretation will be provided by dose and treatment cycle for each visit. Summary statistics for ECG interval data will be provided by dose and treatment cycle for each visit. The number and percentage of subjects in each of the following QTc categories will be provided by dose and treatment cycle for each visit and for any post-treatment visit:

- QTc > 450 msec for males or > 470 msec for females
- QTc > 480 msec
- QTc > 500 msec
- Increase from baseline QTc \geq 30 msec
- Increase from baseline QTc \geq 60 msec

If the ECG is repeated more than once at any timepoint, average of the repeated values will be used for the summary. All ECG results will be included in a listing

9.9. Physical [REDACTED]

A complete physical examination is performed at Screening and Baseline. At post-treatment visits, the physical examination may be abbreviated. Physical [REDACTED] examination results will be summarized by dose and treatment cycle for each visit. All data will be provided in a listing.

9.10. Pulmonary Function Test

Pulmonary function will be recorded using spirometry. Parameters measured are the forced vital capacity (FVC), which is the total volume of air exhaled during forced expiration, and the forced expiratory volume in the first second of exhalation (FEV₁). The FCV and FEV₁ results and changes from baseline will be summarized by dose and treatment cycle for each visit. In addition, the percentage of subjects with a decrease from baseline \geq 10%, \geq 15%, and \geq 20% and an increase from baseline \geq 10%, \geq 15%, and \geq 20% will also be provided. All data will be provided in a listing.

9.11. Dysphagia Severity Score

The presence of dysphagia will be evaluated using the DSS. After the Baseline visit, this scale is collected only if a subject reports swallowing difficulties. The DSS results and changes from baseline will be summarized by dose and cycle for each visit. All data will be provided in a listing.

9.12. Columbia-Suicide Severity Rating Scale

According to the FDA draft guidance for suicidal ideation and behavior ([FDA Guidance Suicidal Ideation and Behavior](#)), the following C-SSRS outcomes, which have yes/no responses, will be sorted in

This document is confidential.

descending frequency of a yes response and numbered to define the composite endpoints for the C-SSRS below:

- Category 1 – Wish to be dead
- Category 2 – Non-specific active suicidal thoughts
- Category 3 – Active suicidal ideation with any methods (not plan) without intent to act
- Category 4 – Active suicidal ideation with some intent to act without specific plan
- Category 5 – Active suicidal ideation with specific plan and intent

- Category 6 – Preparatory acts or behavior
- Category 7 – Aborted attempt
- Category 8 – Interrupted attempt
- Category 9 – Actual attempt
- Category 10 – Completed suicide
- Category 11 – Self-injurious behavior without suicidal intent

A summary table will be provided for each visit by dose and treatment cycle. The summary table will include the yes/no responses to each question in categories 1 through 11 above. In addition, summaries will include any suicidal ideation (highest category with a yes response for categories 1-5 or none if all responses are no), any suicidal behavior (highest category with a yes response for categories 6-10 or none if all responses are no), and any suicidality (highest category with a yes response for categories 1-10 or none if all responses are no), emergence of suicidal ideation (where yes=no suicidal ideation at baseline, and any suicidal ideation at any visit after treatment and no=none), emergence of suicidal behavior (where yes=no suicidal behavior at baseline and any suicidal behavior after treatment and no=none), and worsening of suicidal ideation (yes if most severe suicidal ideation at any post-treatment visit is more severe than the value at baseline for categories 1-5, no if none).

This document is confidential.

[figure not shown]
10. Changes from Analysis Planned in Protocol

[figure not shown]
Additional analyses have been added to determine the impact of COVID-19 on key efficacy variables.

The intent-to-treat and per protocol populations will not be used. As this is an open-label study, only the safety population analysis will be performed. As this is an open-label study, multiple imputation will also not be performed.

[figure not shown]
This document is confidential.

[figure not shown]
This document is confidential.

[figure not shown]
This document is confidential.

[figure not shown]
This document is confidential.

This document is confidential.

This document is confidential.

[figure not shown]
This document is confidential.

13. Quality Control

[figure not shown]
SAS programs are developed to produce output such as analysis data sets, summary tables, data listings, figures or statistical analyses. An overview of the development of programs is detailed in Syneos Health Standard Operating Procedure (SOP) Developing Statistical Programs (3907).

Syneos Health SOPs Developing Statistical Programs (3907) and Quality Deliveries (SDTM, ADaM, TLF) (3908) describes the quality control procedures that are performed for all SAS programs and output. Quality control is defined here as the operational techniques and activities undertaken to verify that the SAS programs produce the output by checking for their logic, efficiency and commenting and by review of the produced output.”

[figure not shown]
This document is confidential.

[figure not shown]
This document is confidential.

[figure not shown]
This document is confidential.

[figure not shown]
This document is confidential.

[figure not shown]
This document is confidential.

[figure not shown]
This document is confidential.

This document is confidential.

This document is confidential.

This document is confidential.

This document is confidential.

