4.3 STUDY VISITS AND TELEPHONE CALLS

[figure not shown]
Figure 3 summarizes the schedule of telephone calls and assessments by treatment cycle.

[figure not shown]
- Screening (Days -21 to -1)
- Baseline Treatment #1, Treatment #2, #3, #4
- Follow-up telephone call after each Treatment:
 - Week 2 after each treatment (study site staff will call the subject)
- Follow-up visits after each Treatment:
 - Weeks 4, 6, 12, and every 4 weeks thereafter until Week 52/End-of-Study Visit (See Figure 1 and Table 1)

[figure not shown]
Safety assessments include laboratory tests (hematology, PT, chemistry, and urinalysis), [REDACTED], [REDACTED], physical and neurological examinations, the C-SSRS, Dysphagia Severity Scale, vital signs, pulmonary function by spirometry, 12-lead ECGs, injection site evaluations, concomitant medications, AE monitoring at protocol-specified timepoints, [REDACTED]

Efficacy assessments, including the TWSTRS (total score and subscale scores), CDIP-58, CGIC, PGIC, TSQ, WPAI, and SF-36 Survey, will be performed at protocol-specified timepoints as outlined in the SOA (Table 1).

No interim analysis is planned for this study.

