8.2.9 COLUMBIA-SUICIDE SEVERITY RATING SCALE

The C-SSRS is a questionnaire that prospectively assesses Suicidal Ideation and Suicidal Behavior using a semi-structured interview to probe subject responses (Appendix H). The C-SSRS is to be administered at each visit, including unscheduled ones. Both the Lifetime/Recent and Since Last Visit versions will be utilized. All assessors will receive formal training in the use of this tool.

A subject who endorses “suicidal ideation” must be referred to a mental health professional for further assessment and/or treatment.

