6.2. Key Definitions

Study day will be assigned as follows:

[figure not shown]
- Before the first study medication dose date, study day = visit date – dose date.
- After the first study medication dose date, study day = visit date – dose date + 1.

The day the study medication is first given is Day 1, and the day before the study medication is first given is considered Day -1.

Unless otherwise specified, baseline value is defined as the last non-missing value before the first study medication administration. Change from baseline is defined as the post-baseline value minus the baseline value (post baseline – baseline). Percent change from baseline is defined as 100 times post-baseline value minus baseline value divided by the baseline value ($100 * (\text{post baseline} - \text{baseline}) / \text{baseline}$).

[figure not shown]
[REDACTED]

This document is confidential.

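### The C-SSRS emergence and worsening summaries use the last pre-dose record as baseline, so ideation or behavior recorded at Screening but not on Day 1 can be counted as new or worse after dosing

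*SAP*

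**What the plan says.** SAP 9.12 derives three C-SSRS summaries by comparing post-dose responses with baseline:

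- The first concerns new ideation: "emergence of suicidal ideation (where yes=no suicidal ideation at baseline, and any suicidal ideation at any visit after treatment and no=none").
- The second applies the same idea to acts rather than thoughts: "emergence of suicidal behavior (where yes=no suicidal behavior at baseline and any suicidal behavior after treatment and no=none").
- The third looks for an increase in severity, over ideation categories 1 to 5: "worsening of suicidal ideation (yes if most severe suicidal ideation at any post-treatment visit is more severe than the value at baseline".

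The section does not say which record, form or recall period supplies the baseline. SAP 6.2 gives the general rule: "Unless otherwise specified, baseline value is defined as the last non-missing value before the first study medication administration".

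Protocol 8.2.9 says of timing: "The C-SSRS is to be administered at each visit, including unscheduled ones". Of the forms it says: "Both the Lifetime/Recent and Since Last Visit versions will be utilized". The available text does not assign the two forms to visits; Table 1 of the protocol, which holds the schedule, is not shown. Protocol 4.3 places the first visit at "Screening (Days -21 to -1"), before treatment on Day 1.

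For rollover subjects first treated in the end-of-study window of Study 1720302, Protocol 4.1 says that the procedures of that end-of-study visit serve as baseline data.

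**The concern.** A last-value baseline suits a laboratory result or a vital sign, where each reading describes the same thing. C-SSRS records are not interchangeable in this way, because the two forms cover different recall periods. Taking the last record may replace a longer look-back with one of a few days.

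Suicidality is a safety topic in which a count of newly emergent cases will be read literally. The trial is open-label without a control arm, so no comparison group would reveal that some emergent cases had ideation on record before dosing.

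The rule also sits awkwardly with the plan's handling of adverse events. Under SAP 9.3, an event that began before dosing is treatment-emergent only if it worsens in severity or is rated as drug-related. Protocol 8.3.1 treats a pre-existing condition as an adverse event only if it worsens. The C-SSRS derivation can drop that requirement.

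**Working it through.** The plan states no figure to reproduce, and no test or sample size is involved. The check applies the SAP rules to the possible response patterns.

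**Look-back of the Day 1 record.** Under SAP 6.2, study day before dosing is visit date minus dose date. Screening on Day -21 is 21 days before dosing, and on Day -1 it is 1 day before. A Since Last Visit form on Day 1 therefore covers 1 to 21 days.

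**Rules.** Score ideation 0 for none and 1 to 5 for the SAP categories. Let S be the Screening value (Recent period), D the Day 1 value and P the highest post-dose value. Assume that Day 1 uses Since Last Visit.

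- SAP baseline: B_last = D
- Alternative baseline: B_worst = max(S, D)
- Emergent: B = 0 and P > 0
- Worsened: P > B

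**Illustrative patterns** (categories chosen only to show each case):

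| S | D | P | Emergent / worsened, B_last | Emergent / worsened, B_worst |
|---|---|---|---|---|
| 3 | 0 | 2 | yes / yes | no / no |
| 2 | 0 | 4 | yes / yes | no / yes |
| 4 | 2 | 3 | no / yes | no / no |
| 3 | 3 | 3 | no / no | no / no |
| 0 | 0 | 2 | yes / yes | yes / yes |

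The first two rows are called emergent although ideation was on record before dosing. The first and third are called worsened although the post-dose category is below the Screening category. The last two rows are classified alike under both rules.

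**Direction.** B_last can never exceed B_worst. Any subject emergent or worsened against B_worst is therefore also emergent or worsened against B_last, and the converse fails. The error can only add cases.

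**Behavior.** The same logic holds: behavior recorded at Screening, none on Day 1 and behavior after dosing is counted as emergent.

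**If Day 1 uses Lifetime/Recent instead.** The Screening history should be captured again and the misclassified patterns should not arise. SAP 9.12 would still not say whether the Lifetime or the Recent answer is the baseline value. A Lifetime baseline would stop anyone with remote history from ever counting as emergent.

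**The case against.** The strongest objection is that the misclassification depends on text that cannot be seen. Table 1 may put Lifetime/Recent on Day 1. The SAP 6.2 default gives way where something else is specified, and redacted material follows it. This stands as a limit on certainty. SAP 9.12 itself shows no redaction at the derivations and no override, and the proposed sentence does no harm if Table 1 turns out favorable.

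Second, last pre-dose value is the SAP's uniform convention, and over-counting is the cautious direction for safety. That is fair as far as it goes. However, a count labelled emergent should not include ideation already on record before dosing.

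Third, the effect is contained. Only three derived summaries are affected, none a primary endpoint under SAP 4.1, and Screening answers remain in the listings under SAP 6.1. This stands and keeps the point minor.

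Stronger readings are tempting, and the documents do not support them:

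- A reader might set the 52-week follow-up against the three-week look-back and infer a large inflation factor. That ratio compares observation windows and is not a miscount rate. Unequal windows come with any summary of events at any post-dose visit.
- A reader might assume a prevalence of ideation and derive a number of miscounted subjects. The documents give no C-SSRS rates, and only subjects who also report ideation or behavior after dosing can be affected.
- A reader might infer that the rollover baseline covers only the time since the previous 1720302 visit. No available text says which form that study used. Nor is it settled which record applies: dosing cannot fall on the end-of-study day, so a Day 1 record may supersede the end-of-study one.
- A reader might conclude that all 1720302 records belong in baseline. SAP 3.4 describes that study as randomized and placebo-controlled, so some subjects had already received DAXI. Pooling its post-dose records could hide ideation that arose after an injection.

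**Conclusion.** The concern holds in a limited, conditional form. On the visible text, SAP 9.12 takes its baseline from SAP 6.2, and that rule ignores every pre-dose C-SSRS record except the last. If the Day 1 form is Since Last Visit, pre-dose ideation or behavior seen only at Screening is lost from the emergence and worsening derivations, and later reports are over-counted.

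The size cannot be estimated. The conclusion rests on three assumptions: that Since Last Visit is used on Day 1; that no unseen text redefines the C-SSRS baseline; and that a rise from no ideation counts as worsening, on which the one-way direction for worsening depends. The first study medication is read as the first dose in this study. The severity is minor, but this is a stated rule that can produce a wrong safety count, which is more than a missing detail.

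**What to change.** Add to SAP 9.12 that, for emergence of ideation, emergence of behavior and worsening of ideation, the C-SSRS baseline is the most severe category over all pre-dose records of this study. These are the Recent period of the Lifetime/Recent form and any Since Last Visit form completed before the first dose in this study. Report Lifetime history separately.

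For rollover subjects, use this study's pre-dose records, or the 1720302 end-of-study record where it serves as baseline. Do not fold other post-dose 1720302 records into baseline. Show rollover and de novo subjects separately in these summaries.

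The cost is a short SAP addition and a small programming change, with no new assessments. The downside is that slightly fewer events may be labelled emergent; the visit-level responses and listings remain available.
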